### 5. Procedures Involved

#### 5.1. Study Design:

Experimental Group: Prospective Cohort of next 30 incoming liver and TPIAT transplant children which meet inclusion criteria. Due to the more difficult predictability of when liver transplants occur, and to ensure adequate enrollment of 30 patients occurs within the 3-year pilot duration, we have chosen not to have a 50/50 balanced prospective cohort.

Control Group: Control will be via retrospective chart review of the last 60 transplant patients from the same population (liver, TPIAT) with same surgeon. Intervention and data collection will be as outlined elsewhere in protocol.

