## MEDICAL PROTOCOL (HRP-590)

PROTOCOL TITLE: Magnesium sulfate as adjuvant analgesia and its effect on opiate use by post-operative transplant patients in the pediatric ICU.

VERSION DATE: 06/09/2022

Control Group: For collection of control data, a MRN list of the most recent 60 transplant patients under the same surgeon at this institution (30 liver, 30 TPIAT) who have not opted out of research will be obtained via UMN's Best Practices Integrated Informatics Core (BPIC), followed by access to EPIC EMR outside of the Information Exchange to review patient's chart and collect for intended outcomes, which are also uploaded into RedCap. This will be done in identical manner as that for prospective data collection — the EMR will be accessed for appropriate patient by MRN, followed by selecting the appropriate surgical encounter by date, followed by selecting only specific portals in epic where intended data elements are located (for example: Intake/Output section, or results review -> magnesium level, etc). Collection of this data will be initiated at the start of IRB approval and ongoing to completion. Full data analysis will be completed at conclusion of study followed by construction of manuscript. Of note, hypomagnesemia is corrected per standard ICU care with IV MgSO4 regardless of study, and liver transplant patients currently have a pre-designed magnesium replacement protocol (also used in our CVICU post-operative cardiac patients). This will still be included in data collection without adjustment to any comparison data in statistical analysis. This replacement protocol will not be used in our study as we will already be providing continuous IV MgSO4. Similarly, magnesium blood levels are checked independent of this study, although will be more frequent now for safety monitoring. These blood levels are drawn through a central line that is already in place independent of this study, so will not require percutaneous needle stick. There are no other drugs/devices involved in study or that would alter MgSO4 delivery.

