### Standard Reporting

2. type of transplant received
3. age
4. weight
5. height
6. gender

*15.2. Power Analysis:* Power analysis was performed based on pediatric studies by Hutchins et al and Jabbour et al (see references section 24), indicating 90 patients in order to see a detectable difference of 20% between study groups with 80% power. This would detect a decrease of nearly 3.5 mg/kg over a 7 day PICU course, and seemed a reasonable target for our hypothesis. Given the progression of IND review, this number will be reduced to 60 for the retrospective cohort (renal transplants removed from study), and 30 for prospective cohort (typical target for pilot-based study), to simulate a pilot study rather than fully correlational study. Regardless, original power analysis is shown below:

n per group	Detectable difference between groups (Total 1st 7 days in morphine equivalent mg/kg)		Detectable difference between groups (% reduction in dose)	
	80% power	90% power	80% power	90% power
40	5.26	6.09	29	33
50	4.70	5.43	26	30
60	4.28	4.95	24	28
70	3.96	4.58	23	26
80	3.70	4.28	21	24
90	3.49	4.03	20	23
100	3.30	3.82	19	22
110	3.15	3.64	18	21
120	3.01	3.49	18	20

Based on a pooled SD estimate for total morphine equivalent dose first 7 days post-op of 8.3 mg/kg (Hutchins 2016), the table lists the minimum differences (in mg/kg) that are detectable with 80% and 90% power for various enrollment sizes. These differences are also presented in terms of the % reduction in total dose, based on an overall mean total dose of 15.5 mg/kg (Hutchins 2016). For comparison, a 29.5% reduction in total dose (first 48h) in ketamine + magnesium versus ketamine was observed in Jabbour 2014.

*15.3. Statistical Analysis:* The primary analysis will compare the total morphine equivalent dose per kg during the PICU stay between experimental and historical control groups. Total dose will be compared in both unadjusted analyses and adjusted analyses using linear models, with a covariate for study group and adjusting covariates for transplant type, age, and gender, to account for potential variation due to these factors. Distributional assumptions will be examined and data transformations will be used as appropriate. Secondary outcomes will be compared using similar approaches using generalized linear models for count

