## **18. Provisions to Monitor the Data to Ensure the Safety of Participants**

## MEDICAL PROTOCOL (HRP-590)

PROTOCOL TITLE: Magnesium sulfate as adjuvant analgesia and its effect on opiate use by post-operative transplant patients in the pediatric ICU.

VERSION DATE: 06/09/2022

*18.1. Data Integrity Monitoring:* The PI and co-investigators will be in direct day-to-day contact (specifics below) throughout the study intervention and with any of the following that arise. The PI and/or co-investigator will have direct notifications any time a transplantation surgery is planned and will confirm that study intervention has been ordered correctly in medical chart on day of PICU admission. Surgery, anesthesia, ICU, and safety monitoring teams will be notified prior to interventions when a patient is confirmed as a study participant. Medical staff will be instructed to page PI and/or co-investigators as well as research coordinator in case of any intervention side effect for further direction. The PI and co-investigators are the most appropriate direct monitors, as both have full understanding of research protocol, and are also frequently in PICU with direct care of these patients. In cases where the PI or co-investigators are not present, deferral will be made to the medical team, which is already adept and required to be following lab results and ensuring nurse orders are carried out. A co-investigator will also otherwise make routine daily lab surveillance for added layer of monitoring. This level of monitoring appears appropriate as once the intervention is ordered in our EMS, nurses carry out the order throughout duration of study. There is no blinding required in this study as all participants will be intended to receive intervention, so there appears no opportunity for bias introduced by the PI or co-investigators while caring for these patients. As patients complete their ICU and conclude their involvement in study, chart reviewer will be notified to update data into REDCap. This will be further overseen by PI and co-investigators. All data collected through chart review will be collected with a standardized data collection form to ensure uniformity.

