22.2. International Research: n/a

## 23. Multi-Site Research: n/a

## 24. Coordinating Center Research: n/a

## 25. Resources Available

25.1. Resources Available: PI and co-investigator have multiple other research colleagues available for assistance if needed. As stated above, it is difficult to predict how many potential participants we will have since transplant is a dynamic field year-to-year, but based on previous years we predict ~10-20 patient per year. The co-investigator (PICU fellow) is allotted multiple blocks each year to research, so most of this time will be devoted to conducting and completing our project, including following up on chart review progress, additional external grant applications, manuscript writing. Multiple other members will also be assisting with various tasks, including a research coordinator who will help with database creation (OnCore and REDCap) and ongoing study monitoring. Data integrity and safety monitoring members are available through UMN services. Biostatistician will be hired through grant funding for data analysis. We anticipate that the combination of these contributors will be enough resource for the project. The UMN Masonic PICU is a 24-bed unit with capability for all current standard-of-care modalities needed in critical care. PI has a fellow office where able to review research data privately. Patients have access to various therapies (PT/OT/ST, music therapy) for their

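### Treatment group is fully confounded with calendar time, and section 15.3 plans no calendar-time analysis to show how far drift in opioid use could explain a difference

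*Combined protocol and SAP*

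**What the plan says.** Section 5.1 defines the experimental arm as "Prospective Cohort of next 30 incoming liver and TPIAT transplant children which meet inclusion criteria" and the comparator in these words: "Control will be via retrospective chart review of the last 60 transplant patients". Section 5.2 fixes the controls at 30 liver and 30 TPIAT cases under the same surgeon at the same institution, with charts abstracted in the same way as for the prospective cohort. No calendar window is given for the controls.

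Section 15.3 compares total morphine equivalents per kg over the PICU stay, unadjusted and in a linear model with study group and "adjusting covariates for transplant type, age, and gender". Significance is judged at a two-sided 5% level, and section 3.1 states an efficacy hypothesis. Section 15 contains no calendar-time term, no look at trend within the controls and no sensitivity analysis for era.

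On timing, section 25.1 states "based on previous years we predict ~10-20 patient per year". Section 5.3 expects enrolment to take about 3 years and reports that it was not approved to begin until July 2020.

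**The concern.** Study group and era are the same variable here: knowing when a child was operated on tells you the arm. If opioid use changed for reasons other than magnesium (co-analgesics, blocks, prescribing policy, case mix), the model assigns that change to magnesium. The three adjusting covariates do not capture it.

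The protocol gives reasons why practice might not be static. Section 2.3 refers to pressure from the opioid crisis and shortage, and section 5.3 to COVID disruption of surgical schedules. Ketamine, paravertebral block and other analgesics are collected under section 15.1, but none is in the primary model. At stake is whether a significant result can be read as evidence about the drug.

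**Working it through.** **Inputs.** From section 15.2: SD 8.3 mg/kg, overall mean 15.5 mg/kg, and a 20% target listed as 3.49 mg/kg at 90 per group and 80% power. From 15.2 and 5.1: 60 controls and 30 treated; section 15.2 says "this number will be reduced to 60 for the retrospective cohort". From 25.1: 10-20 patients per year. From 5.3: about 3 years of enrolment. The annual rate of opioid decline is not in the documents and is assumed. The 7-day figures stand in for the PICU-stay total.

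**Reproducing the plan.** A two-sample t-test with SD 8.3, two-sided 5% and 90 per group gives a detectable difference of 3.49 mg/kg at 80% power, as tabulated. The 20% follows if 15.5 is the mean over both groups: control mean = 15.5 + 3.49/2 = 17.245, and 3.49/17.245 = 20.2%. At the actual 60:30 sizes, power for 3.49 is about 46-47%.

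**Gap between cohorts.** Control span = 60/20 to 60/10 = 3 to 6 years. Gap between midpoints = (control span + enrolment span)/2:
- (3 + 3)/2 = 3.0 years
- (6 + 3)/2 = 4.5 years
- shortest case, 20 per year throughout: (3 + 1.5)/2 = 2.25 years

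**Drift that alone gives the target.** Annual compound decline = 1 - (1 - 0.202)^(1/gap):
- gap 3.0: 7.3% per year (linear: 3.49/3.0 = 1.16 mg/kg per year)
- gap 4.5: 4.9% per year (linear: 3.49/4.5 = 0.78 mg/kg per year)
- gap 2.25: 9.6% per year

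**Smaller drift, no drug effect.** Bias b = 17.245 × (1 - (1 - rate)^gap). SE of the difference = 8.3 × √(1/60 + 1/30) = 1.856. P(significant) = Φ(b/SE - 1.96) + Φ(-b/SE - 1.96).

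| Assumed decline | Bias, mg/kg (gap 3.0 to 4.5) | Share of 3.49 | P(significant) |
|---|---|---|---|
| 1%/yr | 0.51-0.76 | 15-22% | 6-7% |
| 2%/yr | 1.01-1.50 | 29-43% | 8-13% |
| 3%/yr | 1.51-2.21 | 43-63% | 13-22% |
| 5%/yr | 2.46-3.55 | 70-102% | 26-48% |

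At the 2.25-year gap, 2-3% per year gives b = 0.77-1.14 mg/kg, which is 22-33% of the target and a false-positive rate of about 7-9%.

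**What a time-adjusted model can do.** With uniform accrual and one third of patients treated, the between-group variance of time is (2/9) × gap² and the within-group variance is (2/3) × span²/12 + (1/3) × 3²/12. The variance inflation factor (VIF) is the total over the within-group variance.
- Span 3: (2.00 + 0.75)/0.75 = 3.67, r = 0.85, SE 1.856 × √3.67 = 3.55
- Span 6: (4.50 + 2.25)/2.25 = 3.00, r = 0.82, SE 1.856 × √3.00 = 3.21

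The SE rises 1.7-1.9 times. The difference detectable with 80% power is 2.80 × SE, about 9.0-10.0 mg/kg, or 58-64% of 15.5.

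**What the control trend can do.** Slope SE = 8.3/(√60 × span/√12) = 1.24 (3 years) to 0.62 (6 years) mg/kg per year. The 95% half-widths of 2.4 and 1.2 exceed the matching break-even slopes of 1.16 and 0.78. With zero true drift, the interval would exclude break-even with probability P(Z > 1.96 - 1.16/1.24) = 15% to P(Z > 1.96 - 0.78/0.62) = 24%.

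**What recent controls can do.** The latest half spans 1.5-3 years, so the gap falls to (1.5 + 3)/2 = 2.25 or (3 + 3)/2 = 3.0 years, a cut of a quarter to a third. The SE becomes 8.3 × √(1/30 + 1/30) = 2.14.

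**The case against.** The design has real protections: same surgeon and institution, the most recent available cases, identical abstraction, and the same age limits and creatinine exclusion in both groups. Section 15.2 presents the study as a pilot, and section 10.1 frames any reduced target around feasibility. These points reduce the concern. They do not remove it, because none of them holds practice constant over several years and the plan still tests efficacy at 5%.

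A second objection is that the proposed checks cannot settle the matter. That is correct. The time-adjusted model is imprecise, and a flat control trend would not exclude a drift that matters. For the same reason, a rule barring attribution to magnesium whenever drift could explain the result would be close to an automatic veto. The checks are worth having as description only.

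A reader might infer several stronger things that the documents do not support:
- That an ordinary decline would produce the whole effect, or that opioid use in this unit was falling. No rate is given. Section 2.3 cites the crisis and shortage as reasons to seek adjuvants, not as evidence of falling use.
- That surgery date is not collected. The reporting list in section 15.1 starts at item 2 in the text available, the full data list is in an attachment not seen, and section 5.2 selects control encounters by date.
- That the section 18.1 remark, "so there appears no opportunity for bias introduced by the PI or co-investigators", denies era effects. It concerns unblinded care, which is a separate matter.

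**Conclusion.** The point stands as a gap in the analysis plan. Group is completely confounded with calendar time, and section 15.3 neither adjusts for nor describes time. On assumed declines of 2-3% per year, drift supplies about 29-63% of the 3.49 mg/kg target and lifts the false-positive rate to about 8-22%. About 5-7% per year supplies all of it, or about 10% at the shortest gap.

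These sizes rest on the assumed rates, SD 8.3, a normal approximation, and one uniform accrual stream at 10-20 per year. The last is rough: with 30 controls fixed per transplant type, each type has its own unknown span, and the slower one reaches further back. The documents do not show that drift occurred. They show that the plan would not reveal it.

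**What to change.** In section 15.3:
1. Include surgery date in the analysis dataset and report the control date range by transplant type.
2. Plot total morphine equivalents per kg against date within the controls, and estimate the trend with its 95% confidence interval.
3. Pre-specify two sensitivity analyses: (a) the primary model restricted to the most recent half of controls within each transplant type; (b) the primary model plus linear calendar time.
4. State that these are descriptive, that (b) has an SE about 1.7-1.9 times larger and detects only about 9-10 mg/kg, and that a non-significant control trend does not exclude drift.
5. State that a significant group difference will be reported as an association with era and treatment together, hypothesis-generating for the later study, and not as a demonstrated magnesium effect.

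The cost is small: a date already used to find control encounters, one plot and a few extra models. The sensitivity intervals will be wide, and the stated conclusion will be more modest.

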#### 5.2. Study Procedures:

Experimental Group: There will be no operative procedures per study parameters (though the transplantation procedure itself as well as any secondary procedures from complications are otherwise per standard of care). Patient's medical record will be reviewed for basic eligibility criteria (history of myasthenia gravis or heart block). If female and of reproductive age, patient will have a urine B-hCG, which is routine prior to any abdominal surgery. The only prospective study procedure will be the magnesium protocol previously outlined, where IV MgSO4 will be delivered as a 30-minute bolus dose of 50 mg/kg (maximum 2 grams) in OR followed by a 15 mg/kg/hr infusion initiated immediately after (i.e. in OR as well) until conclusion of PICU stay or 48 hours, whichever comes first. Magnesium levels will be monitored throughout the duration of the infusion per above - every 2 hours in OR starting after bolus dose, then every 4 hours [expected window +/- 1 hour]. There are no other baseline visits or follow-up visits independent of the PICU stay and initial consent process. We do not anticipate this study intervention impacting workflow significantly, as infusion medications are standard interventions in the PICU, and these patients already have frequent blood draws. A study schedule with these interventions will be created via OnCore program to ensure compliance with protocol. Data outcomes will be collected from epic EMR at the conclusion of each patient's ICU admission by co-investigator and medical student researcher and stored in REDCap. All collected data is via EMR, so no surveys/scripts/forms are needed for data collection. Specifically, the EMR will be accessed for appropriate transplant patient, followed by selecting the appropriate surgical encounter (which would be current), followed by selecting only specific portals in Epic EMR where intended data elements are located (for example: Intake/Output section, or results review -> magnesium level, etc). Only specific data collection pathways will be targeted while in a patient's medical chart. There are no other drugs/devices involved in study or that would alter MgSO4 delivery. Similarly, there are no out-of-hospital prescriptions or interference during the ICU admission which would alter the study protocol. Any out-of-hospital contact (i.e. pre-admission consent if performed) will include adherence to COVID precautions per hospital guidelines.

## MEDICAL PROTOCOL (HRP-590)

PROTOCOL TITLE: Magnesium sulfate as adjuvant analgesia and its effect on opiate use by post-operative transplant patients in the pediatric ICU.

VERSION DATE: 06/09/2022

Control Group: For collection of control data, a MRN list of the most recent 60 transplant patients under the same surgeon at this institution (30 liver, 30 TPIAT) who have not opted out of research will be obtained via UMN's Best Practices Integrated Informatics Core (BPIC), followed by access to EPIC EMR outside of the Information Exchange to review patient's chart and collect for intended outcomes, which are also uploaded into RedCap. This will be done in identical manner as that for prospective data collection — the EMR will be accessed for appropriate patient by MRN, followed by selecting the appropriate surgical encounter by date, followed by selecting only specific portals in epic where intended data elements are located (for example: Intake/Output section, or results review -> magnesium level, etc). Collection of this data will be initiated at the start of IRB approval and ongoing to completion. Full data analysis will be completed at conclusion of study followed by construction of manuscript. Of note, hypomagnesemia is corrected per standard ICU care with IV MgSO4 regardless of study, and liver transplant patients currently have a pre-designed magnesium replacement protocol (also used in our CVICU post-operative cardiac patients). This will still be included in data collection without adjustment to any comparison data in statistical analysis. This replacement protocol will not be used in our study as we will already be providing continuous IV MgSO4. Similarly, magnesium blood levels are checked independent of this study, although will be more frequent now for safety monitoring. These blood levels are drawn through a central line that is already in place independent of this study, so will not require percutaneous needle stick. There are no other drugs/devices involved in study or that would alter MgSO4 delivery.

### 5.3. Study Duration:

Experimental Group: Enrollment of study participants will be ongoing for entire duration of study as transplant becomes available. The total duration of participant participation will be approximately 1 week, however the length of time in the ICU is dependent on the overall post-operative transplant course, which can vary between patients. The duration anticipated to enroll all study participants is dependent on how long will be required to reach the targeted patient volume of 30, which will likely be approximately 3 years. The circumstances secondary to COVID-19 have made surgical schedules more unpredictable, and therefore a more confirmatory timeline is difficult to infer. Institutional scheduling of elective procedures and approval of patient enrollment did not occur until July 2020. Data analysis should not extend the study duration by more than 2-3 months.

Control Group: Control will be via retrospective chart review of same transplant population. Data analysis and manuscript preparation will follow (ideally with the project being fully concluded by May-June 2023). There is no intended long-term data follow up needed. Data analysis will be performed alongside experimental group data, and is not expected to extend the study duration by more than ~2-3 months.

## MEDICAL PROTOCOL (HRP-590)

PROTOCOL TITLE: Magnesium sulfate as adjuvant analgesia and its effect on opiate use by post-operative transplant patients in the pediatric ICU.

VERSION DATE: 06/09/2022

5.4. Use of radiation: n/a

5.5. Use of Center for Magnetic Resonance Research: n/a

## 6. Data and Specimen Banking - n/a

## 7. Sharing of Results with Participants

7.1. Summary data from all participants will be created to acknowledge study participation and inform patients/parents of study conclusions once complete. No identifying information will be shared. Magnesium levels and overall pain requirements will be shared on daily family-centered rounds, however this is in accordance with standard information sharing with patients/families and is independent of research study.

